15.1.4. SENSITIVITY ANALYSIS OF PRIMARY EFFICACY VARIABLE

As sensitivity analysis, the primary endpoint will also be analyzed on the PPS with the combination of NRI and MI methods as the missing data method (described in section 15.1.2.4) using M1 as for the primary analysis.

15.2. SECONDARY EFFICACY

15.2.1. SECONDARY EFFICACY VARIABLES & DERIVATIONS

15.2.1.1. PASI 75

The proportion of patients with a PASI 75 response will be assessed at Week 24.

The derivation of PASI 75 is detailed in section 15.1.1.

15.2.1.2. Improvement in PASI

The mean percentage improvement in PASI at Week 16 will be assessed.

15.2.1.3. sPGA

The proportion of patients with a sPGA ≤ 1 (clear or almost clear) at Week 16 will be assessed.

15.2.1.4. DLQI

The proportion of patients achieving a DLQI of 0 or 1 at Week 16 will be assessed.

15.2.2. MISSING DATA METHODS FOR SECONDARY EFFICACY VARIABLE(S)

Missing PASI 75 at Week 24 as well as missing sPGA and DLQI at Week 16 will be imputed using the combination of NRI and LOCF methods as missing data method considering NRI at Week 24 or Week 16 according to the variable considered (see Section 15.1.2.4).

Document: \\ieedc-nas01a:\Boehringer_Ingelheim\BI_695501\XXA39605\Biostatistics\Documentation\SAP\15-v2.0\BI 1297.12 SAP v2.0 31JAN2018.docx

Author: Version Number: 2.0
Version Date: 31JAN2018

Template No: CS_TP_BS016 Revision 4
Effective Date: 01Apr2016

Reference: CS_WI_BS005

15.2.3. ANALYSIS OF SECONDARY EFFICACY VARIABLES

All secondary analyses will be based on FAS.

15.2.3.1. PASI 75, sPGA and DLQI analysis

The risk difference will be estimated using the method of Reeve with a 95% significance level (see Section 15.1.3).

15.2.3.2. Improvement in PASI

For the percentage improvement from baseline in PASI, analysis of covariance (ANCOVA) will be used, comparing the mean percentage improvement from Baseline of PASI between BI 695501 versus US-licensed Humira at Week 16. The estimate of the difference will be computed with its 95% CI.

ANCOVA will be performed based on the following model:

(M2) PASI percentage improvement from baseline at Week 16 = Treatment + Baseline PASI + Prior exposure to a biologic agent + random error

Document: \\eedc-nas01a:\Boehringer_Ingelheim\BI_695501\XXA39605\Biostatistics\Documentation\SAP\15-v2.0\BI 1297.12 SAP v2.0 31JAN2018.docx

Author: Version Number: 2.0
Version Date: 31JAN2018

Template No: CS_TP_BS016 Revision 4
Effective Date: 01Apr2016

Reference: CS_WI_BS005

Document: \\eedc-nas01a:\Boehringer_Ingelheim\BI_695501\XXA39605\Biostatistics\Documentation\SAP\15
-v2.0\BI 1297.12 SAP v2.0 31JAN2018.docx

Author: Version Number: 2.0
Version Date: 31JAN2018

Template No: CS_TP_BS016 Revision 4
Effective Date: 01Apr2016

Reference: CS_WI_BS005

16. SAFETY OUTCOMES

All outputs for safety outcomes will be based on the SAF for overall and Period 1 outputs.

There will be no statistical comparisons between the treatment groups for safety data, unless otherwise specified with the relevant section.

Safety will be assessed as a secondary objective in this trial.

The safety endpoint is defined as the proportion of subjects with drug-related AEs. This safety endpoint is considered a secondary endpoint in this trial.

Other safety endpoints are:

- Proportion of patients with AEs, SAEs, and AESIs

16.1. ADVERSE EVENTS

Adverse Events (AEs) will be coded using MedDRA central coding dictionary, Version 19.1 or higher. The system organ classes will be sorted by internationally agreed EMA SOC order (refer to APPENDIX 3); preferred terms will be sorted by decreasing frequencies (within system organ class).

A summary of the number of subjects and percentages within each of the categories described in the sub-section below will be provided.

In case of worsening in severity, a new entry is created with start date equal to start of worsening.

Listings will include Treatment-Emergent Adverse Events (TEAEs) and Non-TEAEs.

16.1.1. ADVERSE EVENT SPECIFIC DERIVATION

16.1.1.1. Treatment Emergent Adverse Event

Treatment-Emergent Adverse Events (TEAEs) are defined as AEs that started or worsened on or after the first dose of trial medication and prior to the last date of trial medication + 10 weeks (70 days) inclusive.

There is one specific period of interest:

- Period 1 starts on the first administration day (Day 1 visit) and finishes prior to the visit date of Day 113 visit.

Period 1 Treatment-Emergent Adverse Events (P1 TEAEs) are defined as AEs that started or worsened on or after the first dose of trial medication during period 1 and prior to or at the last date of trial medication during period 1 + 10 weeks (70 days) inclusive.

Non-TEAEs will be classified as "Screening" if AE start date is strictly prior the first injection date. Non-TEAEs will

Document: \\ieedc-nas01a:\Boehringer_Ingelheim\BI_695501\XXA39605\Biostatistics\Documentation\SAP\15-v2.0\BI 1297.12 SAP v2.0 31JAN2018.docx

Author: Version Number: 2.0
Version Date: 31JAN2018

Template No: CS_TP_BS016 Revision 4
Effective Date: 01Apr2016

Reference: CS_WI_BS005

be classified as “Post treatment” if AE start date is strictly after the last injection date + 70 days.

See APPENDIX 2 for handling of partial dates for AEs. In the case where it is not possible to define an AE as treatment-emergent or not, the AE will be classified by the worst case, i.e., treatment-emergent in the period of the last injection of trial medication.

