4.1.4 Drug assignment and administration of doses for each patient

Each patient will receive 80 mg of BI 695501 or US-licensed Humira at the Baseline Visit (Day 1, Week 0) followed by 40 mg of BI 695501 or US-licensed Humira 1 week later, and then 40 mg of BI 695501 or US-licensed Humira every other week until Week 16 (primary endpoint).

After Week 16 (Day 112), patients achieving at least a PASI 50 response will continue receiving their randomized treatment (40 mg BI 695501 or Humira every other week) until Week 24 in a blinded fashion.

Patients not achieving at least PASI 50 at Week 16 will not be further treated with the study drugs, but only followed up for safety.

The prefilled syringe must be removed from refrigeration 30 minutes before administration to permit the medication to warm. Injecting cold medication can cause discomfort. Once taken out of the refrigerator, the trial medication should be administered within 1 hour. A syringe must not be used if it is frozen or if it has been left in direct sunlight.

The patient will administer the injection in an area of the skin where post-administration assessments of any reaction would not be compromised by the presence of impairment to skin integrity. The location for the trial medication injection will be the lower abdomen (excluding a 2-inch [5-cm] area around the navel) and upper thigh. A different injection site should be selected for each injection (at least 1 inch [2.5 cm] away from the previous site).

For the duration of the trial, trial medication will be administered either at the trial site by dedicated trial personnel, or at home by the patients themselves. At all designated site visits (Weeks 0 and 1), the patient must administer BI 695501 while at the trial site. Between designated site visits (Weeks 3, 5, 7, 9, 11, 13, 15, 17, 19, 21, and 23), the patient may choose to come to the site to self-inject the trial medication with the support of suitably qualified, designated trial site personnel or the patient may self-inject the trial medication at home. Patients will be instructed to accurately record the dates and times of dosing, problems encountered with dosing, the occurrence of any AEs, the use of concomitant therapies, and the prefilled syringe storage conditions on the provided diary cards between the trial site visits.

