3. TRIAL DESIGN

3.1. GENERAL DESCRIPTION

This is a multinational, randomized, double-blind, parallel-arm, multiple-dose, active comparator trial of BI 695501 and US-licensed Humira.

In total, approximately 300 patients with moderate to severe chronic plaque psoriasis are planned to be randomized in this trial.

Document: \\ieedc-nas01a:\Boehringer_Ingelheim\BI_695501\XXA39605\Biostatistics\Documentation\SAP\15
-v2.0\BI 1297.12 SAP v2.0 31JAN2018.docx

Author: Version Number: 2.0
Version Date: 31JAN2018

Template No: CS_TP_BS016 Revision 4
Effective Date: 01Apr2016

[figure not shown]
Reference: CS_WI_BS005

Patients are included in the trial once they have signed the informed consent. Patients suitable after screening will be eligible to participate in the 24-week treatment period and will be randomized at a ratio of 1:1 in a blinded fashion to 1 of 2 treatment arms (BI 695501 or US-licensed Humira).

After Week 16, only patients who achieve at least a 50% reduction in Psoriasis Area and Severity Index (PASI 50) response will continue the trial receiving their randomized treatment up to Week 24. Those patients not achieving at least PASI 50 (or who discontinue the trial early), will not be treated with the trial drugs, but only followed up for safety.

All patients who receive at least 1 injection of BI 695501 will have a Safety Follow-up visit 10 weeks after the last dose of trial medication.

Diagram of trial design

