9. DISPOSITION AND WITHDRAWALS

All subjects who provide informed consent will be accounted for in this trial.

The counts of the analysis sets will be presented:

- All Subject Enrolled Set (ENR)
- All Subjects Randomized Set (RND)
- Full Analysis set (FAS)
- Per Protocol Analysis Set (PPS)
- Safety Analysis Set (SAF)
-

The reasons for exclusion from the analysis sets will be listed.

The following subject disposition and withdrawals will be presented for the ENR set:

Document: \\ieedc-nas01a:\Boehringer_Ingelheim\BI_695501\XXA39605\Biostatistics\Documentation\SAP\15
-v2.0\BI 1297.12 SAP v2.0 31JAN2018.docx

Author: Version Number: 2.0
Version Date: 31JAN2018

Template No: CS_TP_BS016 Revision 4
Effective Date: 01Apr2016

Reference: CS_WI_BS005

Statistical Analysis Plan

- Screened
- Rescreened
- Screen failure (defined as withdrawn from trial prior to randomization). The information will be displayed only once for subjects being rescreened and will correspond to the last information available in the eCRF.
- Primary reason for non-inclusion. The information will be displayed only once for subjects being rescreened and will correspond to the last information available in the eCRF.
- Randomized
- Randomized but not treated
- Treated
- Subjects with PASI 50 at Day 113 (Week 16)
- Subjects treated after Day 113 (Week 16)
- Completed treatment at Day 169 (Week 24)
- Completed the trial
- Discontinued from treatment strictly before Day 113 (Week 16), primary reason for premature discontinuation from treatment before Day 113 (Week 16)
- Discontinued from treatment, primary reason for premature discontinuation from treatment
- Discontinued from trial, primary reason for premature discontinuation from trial

The following subject disposition and withdrawals will be presented for the ENR set per site:

- Screened
- Rescreened
- Screen failure (defined as withdrawn from trial prior to randomization). The information will be displayed only once for subjects being rescreened and will correspond to the last information available in the eCRF.
- Randomized

Document: \\ieedc-nas01a:\Boehringer_Ingelheim\BI_695501\XXA39605\Biostatistics\Documentation\SAP\15-v2.0\BI 1297.12 SAP v2.0 31JAN2018.docx

Author: Version Number: 2.0
Version Date: 31JAN2018

Template No: CS_TP_BS016 Revision 4
Effective Date: 01Apr2016

Reference: CS_WI_BS005

- Randomized but not treated
- Treated
- Subjects with PASI 50 at Day 113 (Week 16)
- Subjects treated after Day 113 (Week 16)

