13. TRIAL MEDICATION EXPOSURE

Exposure to trial medication will be presented at Primary Analysis for the SAF, at Final Analysis for the FAS, PPS and SAF.

The proportion of subjects treated at each planned visit (administration on Day 1, Day 8, and every other week until Day 162) and per treatment group will be presented.

Descriptive statistics for the number of injections from Day 1 up to Week 16 (included), from Week 16 (excluded) up to Week 24 and overall per subjects will be presented.

Number of subjects per duration of exposure categories, patient time (years) per duration of exposure categories, and descriptive statistics for duration of exposure will be presented.

Document: \\eedc-nas01a:\Boehringer_Ingelheim\BI_695501\XXA39605\Biostatistics\Documentation\SAP\15-v2.0\BI 1297.12 SAP v2.0 31JAN2018.docx

Author: Version Number: 2.0
Version Date: 31JAN2018

Template No: CS_TP_BS016 Revision 4
Effective Date: 01Apr2016

Reference: CS_WI_BS005

Exposure categories will be the following cumulative categories: ≥ 1 day, ≥ 2 weeks, ≥ 4 weeks, ≥ 12 weeks, ≥ 16 weeks, and ≥ 24 weeks.

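### Period 1 closes before the Day 113 visit, but Period 1 TEAEs run to about Day 176, so for patients who continue the Period 1 adverse event tables include events after all four post-Week-16 doses

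*SAP*

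**What the plan says.** SAP section 16.1.1.1 defines one period of interest: "Period 1 starts on the first administration day (Day 1 visit) and finishes prior to the visit date of Day 113 visit". The sentence after it defines a Period 1 TEAE as an AE that starts or worsens on or after the first dose and "prior to or at the last date of trial medication during period 1 + 10 weeks (70 days) inclusive". The overall TEAE definition in the same section uses the same tail, counted from the last dose of all: "prior to the last date of trial medication + 10 weeks (70 days) inclusive".

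Dosing is described in SAP section 13 as "administration on Day 1, Day 8, and every other week until Day 162". SAP section 3.1 says that patients with at least a PASI 50 response at Week 16 "will continue the trial receiving their randomized treatment up to Week 24"; the others receive no further trial drug.

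The Period 1 window feeds these outputs, each given overall and for Period 1:
- SAP 16.1.2: all TEAEs, with breakdowns by intensity and relationship
- SAP 16.1.3: TEAEs leading to discontinuation of trial medication
- SAP 16.1.4: serious, related serious and frequent non-serious events

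SAP section 12 has a separate Period 1 rule for concomitant medication. The medication must have started before the Week 16 visit date, and there is no 70-day tail.

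**The concern.** A table labelled Period 1 will be read as the safety experience up to the Week 16 visit, when every patient was due to receive the randomized drug. If the window runs 70 days past the last Period 1 dose, then for a patient who goes on to the Week 17 dose it also takes in AEs that arise under later doses. Three things follow.

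- The tables would mix a phase planned for all randomized patients with a phase open only to those with at least a PASI 50 response.
- No second period is defined, so the planned AE tables would offer no summary of the Week 16 to Week 24 phase.
- The primary analysis is cut at the last patient's Week 16 visit (SAP section 4.1), so Period 1 counts would depend on how early each patient enrolled.

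**Working it through.** **Inputs**
- Dosing weeks 0, 1, 3, 5, 7, 9, 11, 13, 15, 17, 19, 21 and 23 (Protocol Flow Chart and section 4.1.4; SAP section 13).
- Study day = 7 × week + 1, which gives Days 1, 8, 22, 36, 50, 64, 78, 92, 106, 120, 134, 148 and 162.
- Period 1 ends before the Day 113 visit, so it is nominally Days 1 to 112.
- Tail of 70 days (SAP section 16.1.1.1).

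**Reproducing the plan's own figure.** Last planned dose + 70 = 162 + 70 = Day 232. This is the safety follow-up day in the Flow Chart, so the day count is being applied as the plan intends.

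**The same rule for Period 1**
- Last dose before Day 113 = Day 106 (Week 15).
- End of window = 106 + 70 = Day 176. With the ±2-day visit window at Week 15, this is Day 174 to Day 178.
- Doses between Day 113 and Day 176: Days 120, 134, 148 and 162, which are all of the later doses.
- Days beyond Period 1 = 176 − 112 = 64, and 64/112 = 57%.
- The Week 16 to Week 24 phase (Days 113 to 169) is 57 days. All of it lies in the window, with 7 days to spare.
- Share of the overall window = 176/232 = 76%, leaving 232 − 176 = 56 days outside.

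**Which patients.** For a patient whose last dose of all falls in Period 1, the 70 days are the ordinary residual effect period (Protocol sections 5.3.6.2 and 7.3.4). The mismatch arises in patients dosed again after Week 16. Among them it arises whenever the last Period 1 dose was Day 50 or later: 50 + 70 = 120, which is past Day 113, while 36 + 70 = 106 is not.

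**Set against SAP section 12.** Take a continuing patient with an AE that starts on Day 150 and is treated with a drug started that day. Since 150 ≤ 176, the AE is a Period 1 TEAE. The drug started after the Week 16 visit, so it is not a Period 1 medication.

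**At the primary analysis cut-off.** The last patient is then at about Day 113. A continuing patient who started d days earlier is at Day 113 + d and reaches Day 176 when d = 176 − 113 = 63 days, or 9 weeks. Continuing patients who started at least 9 weeks before the last one therefore contribute the full 176 days, and later starters contribute between 113 and 176.

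**The case against.** **The wording could be read another way.** The phrase *during period 1* occurs twice in the sentence. Its first occurrence might limit the onset of the AE, since there is only one first dose and it needs no such qualifier. The rule for undatable AEs, which places them in the period of the last injection, also hints that each event was meant to sit in one period. On that reading, events after Week 16 are already excluded. This is strained. The second occurrence attaches to the last date of trial medication, and if onset were limited to Period 1 the 70-day limb would matter only for patients who stopped early. The text does not say so.

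**The tail has a protocol basis.** AEs within 10 weeks of the last dose count as on treatment. That stands for patients who stop. It does not carry over to patients dosed again at Week 17, because the residual period runs from the last dose and Week 15 is not their last dose.

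**Changes at the final analysis are announced.** SAP section 4.2 says that the analyses will be repeated on partly updated data, safety data in particular. Uneven follow-up at the cut-off also affects the overall TEAE tables and applies to both arms. All of this is true. But a window that closes at Week 16 would be complete for every patient at that cut-off, apart from data updates, and this one is not.

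**Stronger readings that the documents do not support.** A reader might infer any of the following:
- *That every Period 1 safety output is affected.* The rule governs AE tables; concomitant medication has its own Week 16 limit.
- *That the Period 1 tables nearly duplicate the overall ones.* The window is 76% of the overall window, and the documents give no event counts from which to judge the overlap of events.
- *That events are credited to the wrong drug.* Patients stay on their randomized treatment.
- *That the safety endpoint is compromised.* The proportion of patients with drug-related AEs is not restricted to Period 1.

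**Conclusion.** The concern holds for the Period 1 AE tables and for patients dosed after Week 16. As written, their window is nominally 176 days instead of 112, it includes all four later doses, and it conflicts with the Period 1 rule for concomitant medication. Period 1 counts can rise between the primary and the final analysis because of follow-up after Week 16.

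The primary efficacy analysis, the overall TEAE tables, the drug-related AE endpoint and the comparison by randomized arm are untouched, and the safety analyses are descriptive. This is a defect in what the Period 1 tables mean, worth correcting but no threat to the equivalence conclusion.

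The conclusion rests on the nominal dosing days and on the literal reading of the sentence. It also assumes that the cut-off implementation document named in SAP Appendix 4, which is not reproduced, adds no cap. The visible text contains none.

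**What to change.** Define a Period 1 TEAE as an AE that starts or worsens from the first dose to the day before the Day 113 visit (nominal Day 113 if there was no such visit), or to last dose + 70 days if that is earlier. Later events stay in the overall TEAE tables, which keep their 70-day rule.

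This version also drops residual-period events after Week 16 in patients whose last dose fell in Period 1. SAP section 16.1.7 already tabulates events after the last injection for those stopped for lack of efficacy. If the sponsor wants such events kept in the Period 1 tables, the cap can apply only to patients dosed after Week 16, with a footnote stating the two windows. Counts for patients who stopped shortly before the cut-off could then still grow by the final analysis.

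Either version costs one SAP sentence and one date condition in the programs. The downside is that Period 1 counts become smaller.

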16.1.1.2. Risk ratio

Risk ratios and associated 95% exact confidence interval will be presented for adverse events of special interest.

Risk ratio will be defined as: $[a/(a+b)]/[c/(c+d)]$

where:

1. **a** is the number of subjects with AESI within treatment group BI 695501
2. **a+b** is the total number of subjects in treatment group BI 695501
3. **c** is the number of subjects with AESI within treatment Humira
4. **c+d** is the total number of subjects in treatment group Humira

PROC FREQ with option RELRISK will be used for programming purpose.

```
proc freq data=data_AESI;  
    tables AESI_WITH_CRITERION*TRT;  
    exact relrisk(method=score);  
    weight count;  
run;
```

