Comparator products:	US-licensed Humira, solution for s.c. injection in single-use prefilled syringe (40 mg)		
dose:	Starting 1 week after a first administration of 80 mg Humira after randomization, patients will receive 40 mg every other week via a single prefilled glass syringe.		
mode of administration:	Subcutaneous injection		
Duration of treatment:	Patients are planned to be treated with trial medication for 24 weeks. Seven days after a first 80 mg administration of either BI 695501 or US-licensed Humira, patients will receive 40 mg of either BI 695501 or US-licensed Humira every other week up to efficacy assessment at Week 16. Only patients achieving at least a PASI 50 response will continue the treatment after 16 weeks, ending at Week 24.		
Endpoints	
Efficacy endpoints will be measured at Week 16 (equivalence assessment) and Week 24.
 
Primary efficacy endpoint:
 
 Proportion of patients with a 75% reduction in Psoriasis Area and Severity Index (PASI 75) response at Week 16 
Secondary endpoints:
 
Efficacy
 
 Proportion of patients with a PASI 75 response at Week 24 Mean percentage improvement in PASI at Week 16 Proportion of patients with a sPGA ≤ 1 (clear or almost clear) at Week 16 Proportion of patients achieving a Dermatology Life Quality Index (DLQI) of 0 or 1 at Week 16 
Safety
 
 Proportion of patients with drug-related adverse events (AEs) 		
Safety criteria:	Physical examination, vital signs (blood pressure, pulse rate, body temperature), 12-lead electrocardiogram (ECG), laboratory tests, continuous AE monitoring, and local tolerability.		
Statistical methods:	
Primary analysis
 
To conclude equivalence, the 95% confidence interval (CI) of the difference in PASI 75 response rate at Week 16 between BI 695501 and Humira must be fully
		

Name of company:		Boehringer Ingelheim	
Name of finished product:		NA	
Name of active ingredient:		BI 695501	
Protocol date: 26 Apr 2016	Trial number: 1297.12		Revision date:
		within the equivalence limits of $\pm 18\%$. Secondary analysis For the secondary efficacy endpoints, point estimates (risk difference for binary endpoints) and CIs will be calculated, but will be interpreted in a descriptive manner. Safety endpoints and AESIs will be presented descriptively. Risk ratio together with 95% CI will be presented for the secondary safety endpoint.	

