7.3.2.2 Secondary Safety Endpoints

The secondary endpoint is:

- Proportion of patients with drug-related AEs.

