Safety analyses will be descriptive in nature. No formal inferential analyses are planned for safety comparison. The analyses will be on the SAF. Frequency of adverse events will be tabulated overall and by system organ class and preferred term after coding according to the current version of MedDRA. In addition, risk ratio together with 95% CIs will be presented for the overall proportion.

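### The visible SAP plans risk ratios only for AESIs and does not carry over the descriptive risk ratio with 95% CI that the protocol synopsis promises for drug-related AEs, the only secondary safety endpoint

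*SAP*

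**What the plan says.** **Protocol.** Section 7.3.2.2 lists one secondary safety endpoint: "Proportion of patients with drug-related AEs". The synopsis, under statistical methods, makes safety endpoints and AESIs descriptive and then adds: "Risk ratio together with 95% CI will be presented for the secondary safety endpoint". Section 7.3.4 rules out formal inference for safety but, after describing AE tabulations, says that "risk ratio together with 95% CIs will be presented for the overall proportion".

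**SAP.** Section 16 keeps the same endpoint and calls it secondary: "The safety endpoint is defined as the proportion of subjects with drug-related AEs". It also sets a default: "There will be no statistical comparisons between the treatment groups for safety data, unless otherwise specified with the relevant section". Section 16.1.1.2 is the only visible place where a safety risk ratio is specified: "Risk ratios and associated 95% exact confidence interval will be presented for adverse events of special interest". The numerator a in its formula "is the number of subjects with AESI within treatment group BI 695501", c is the Humira counterpart, and the code reads an AESI dataset.

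For drug-related events, SAP 16.1.2 plans subject counts, percentages and event counts by SOC and PT, split by relationship, overall and for Period 1. Section 16.1.2.2 defines a related event, treats a missing relationship as related, and plans a listing.

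**The concern.** Comparing the safety profiles of the two products is a stated secondary objective, and drug-related AEs are the one safety outcome that both documents raise to secondary status. The protocol says how the arms are to be contrasted on it, while the SAP applies that contrast to another set of events. A programmer following the SAP would produce risk ratios for AESIs and none for the named endpoint. The clinical trial report would then lack an estimate that the protocol commits to. Anyone wanting it would have to derive it afterwards, with the population, period, direction and interval method not fixed in advance.

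**Working it through.** The point rests on comparing text, not on a figure stated in the plan.

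| Item | Protocol | Visible SAP |
|---|---|---|
| Secondary safety endpoint | Drug-related AEs (7.3.2.2) | Drug-related AEs (16) |
| Risk ratio with CI for that endpoint | Yes (synopsis) | Not specified |
| Risk ratio with CI for AESIs | Not specifically promised; descriptive (synopsis) | Yes, exact 95% CI (16.1.1.2) |
| Risk ratio with CI for an overall proportion | Yes (7.3.4) | Not specified |
| Default for other safety contrasts | Descriptive, no formal inference (7.3.4) | None unless a section specifies one (16) |

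Step 1. The endpoint is the same in both documents, so a changed definition does not explain the difference.

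Step 2. SAP 16.1.1.2 refers to AESIs in its opening sentence, in the definitions of a and c, and in the code. Drug-related AEs cannot be read into it.

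Step 3. The SAP default excludes any contrast that a section does not name. Neither 16.1.2 nor 16.1.2.2 names one.

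Step 4. SAP section 1 says it is based on protocol version 1.0, the version quoted here. No visible text records or explains a change.

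**Size of the missing estimate.** Inputs: about 300 patients randomized 1:1 (protocol synopsis), so n = 150 per arm; two-sided 95% level (SAP 6.5). The drug-related AE risk q is an assumption, because the documents give none. With equal risks (true ratio 1) and the usual large-sample interval on the log scale:

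SE(log RR) = sqrt(2(1 − q)/(q × n)); 95% CI = exp(±1.96 × SE)

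- q = 10%: SE = sqrt(2 × 0.90/(0.10 × 150)) = sqrt(0.1200) = 0.346; CI 0.51 to 1.97
- q = 20%: SE = sqrt(2 × 0.80/(0.20 × 150)) = sqrt(0.0533) = 0.231; CI 0.64 to 1.57
- q = 30%: SE = sqrt(2 × 0.70/(0.30 × 150)) = sqrt(0.0311) = 0.176; CI 0.71 to 1.41
- q = 40%: SE = sqrt(2 × 0.60/(0.40 × 150)) = sqrt(0.0200) = 0.141; CI 0.76 to 1.32

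These figures show that the estimate can be obtained from data already planned, and how precise it would be. They do not measure bias or lost power.

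**The case against.** The strongest reply is that safety is descriptive by design. No margin, test or decision depends on this ratio, and the endpoint itself, a proportion, is still summarized by arm. If the tables include a row for any related TEAE, a reader can compute the ratio from the counts and arm sizes. The output templates that accompany the SAP are not available here, and parts of the SAP are missing from the text supplied, so a risk ratio row or a note of changes from the protocol could exist there.

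Much of this stands, and it limits the point. It does not remove the conflict, because the protocol includes the risk ratio within its descriptive reporting: the synopsis and 7.3.4 both pair descriptive safety with a ratio and interval. A ratio that readers could work out for themselves is not the presented estimate that was promised. A row in a template would still leave SAP 16.1.1.2, the section that fixes the method, without this endpoint.

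Four stronger readings are tempting, and the documents do not support them:

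- *The safety objective gets no between-arm estimate.* The AESI risk ratios are such estimates.
- *The endpoint is dropped.* It is kept as secondary and tabulated by arm; only the contrast is missing.
- *Protocol 7.3.4 makes the same promise for drug-related AEs.* Its sentence follows one on the frequency of adverse events in general, so the overall proportion may mean patients with any AE. Only the synopsis is explicit.
- *AESIs will be too sparse for their ratios to inform.* This may prove true, but neither document gives an expected AESI rate.

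**Conclusion.** In its limited form the point holds. The protocol synopsis commits to a descriptive risk ratio with 95% CI for the only secondary safety endpoint, and the visible SAP plans risk ratios only for AESIs. One named endpoint therefore has no planned between-arm estimate. If the overall proportion in protocol 7.3.4 means any AE, that ratio is missing as well.

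The consequence is confined to descriptive safety reporting: neither the equivalence conclusion nor data collection is touched. The interval widths above depend on assumed event rates, equal risks and 150 patients per arm. The finding of omission depends on the SAP text that can be seen.

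**What to change.** In SAP 16.1.1.2, add the risk ratio (BI 695501 / Humira) with 95% CI for the proportion of patients with at least one drug-related TEAE, on the SAF, from first dose through the 10-week residual effect period. Name it as the descriptive analysis of the secondary safety endpoint and state the interval method. Keep the AESI ratios.

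State what the overall proportion in protocol 7.3.4 refers to. If it means patients with any AE, present the same ratio for patients with any TEAE. If the sponsor intends to report no such ratios, record the departure from the protocol with a reason.

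The existing code should not be copied unchanged. It places the event in the rows and treatment in the columns, whereas the PROC FREQ relative risk compares rows. For illustration, with 6/150 against 3/150 the ratio defined in the SAP is 2.00, but comparing the event row with the no-event row for the BI 695501 column gives (6/9)/(144/291) = 1.35. Treatment should be the row variable.

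Cost: one sentence and one or two table rows, with no new data and no effect on the primary conclusion.
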